THE BIDMC is the coordinating site, and Core B (Epidemiology Core), Project 2 (Biomarkers), Project 3 (Neuroimaging) are based at the BIDMC. The work of the 4 projects and 3 supporting cores, across 3 study sites, will be interconnected and synergistic, and will be coordinated through the Administrative Core (Core A). Under the leadership of [name] (BIDMC investigator), this Core will provide the leadership and organization that will ensure integration, efficiency, and productivity; provide fiscal and budgetary management; verify scientific progress and adherence to timelines; provide safety monitoring; and coordinate all relevant meetings and reporting activities. The administrative components to achieve these goals will include the Steering Committee, meeting monthly to oversee the entire project; Operations Committee, meeting weekly to handle day-to-day progress of the cohort assembly and data collection; Fiscal Management Committee, meeting quarterly to oversee all budgets/subcontracts; Scientific Advisory Board, meeting yearly to evaluate progress; and a Safety Officer, meeting semiannually to oversee the safety monitoring plan.

B10 Dissemination of Research Results

We are sending out newsletters 1-2 times a year thanking participants for their participation. Whenever possible we will include progress and results of the study.

LITERATURE CITED

- The Administration on Aging (AOA). A profile of older Americans. Washington, DC: American Association of Retired Persons, 1995.

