A.3.1. Study Procedures: The study procedures, including screening, baseline, hospital, and follow-up assessments are detailed below. All face-to-face assessments will be conducted either in the subject's place of residence or in the out-patient clinics, according to the convenience and preference of the subject. Our previous studies and pilot work support our ability to accomplish the proposed study procedures. [name] have conducted previous studies that have utilized all the proposed methods. Moreover, we will put into place back-up methods, such as revisits, tailoring time and procedures, and follow-ups by the study investigators themselves to assure completion of all steps. In [name] previous study of over 919 frail medical patients (*[name] 1999 NEJM*), complete follow-up at 12 months was available in 81% of subjects, with 17% lost due to mortality and only 2% true losses to follow-up. The feasibility interviews will be conducted over the phone.

A.3.1.1. Research staff: All research staff, comprised of research nurses and experienced clinical research interviewers, will undergo intensive training, following standardized procedures, in all questionnaires and research methods. They will be carefully trained to handle emergency issues in the home setting, and the project and core leaders will be available to provide back-up at all times. Baseline standardization and inter-rater reliability assessments will be conducted to verify consistency of all staff on the primary outcomes (including the neuropsychological test battery and functional outcomes), as well as key risk factor variables (including the delirium assessment). Interviewer quality checks with inter-rater reliability assessments on all key study variables will be performed every 6 months for the duration of the study.

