A.3.1.4. Hospital assessments: The purpose of the hospital assessment is to monitor daily for development of delirium and to assess precipitating factors. We anticipate that all patients in the surgical group will be hospitalized. Automatic systems will be in place to notify the principal investigator immediately whenever an enrolled study patient is admitted to the BIDMC or BWH. Upon admission, the patient will be seen by the study team in the hospital, and will undergo daily 10-15 minute interviews including a cognitive screen, digit span test, CAM, DSI, and MDAS ratings. Precipitating factors (e.g., infections, immobilization, surgical procedures, post-surgical complications) will be assessed by interview and review of the medical record using standardized, validated methods applied in our previous studies. The initial hospitalization during the study period will be considered the index hospitalization (admission will be zero-time), and the timing of follow-up will begin from this time. For study purposes readmission within 24 hours is considered a continuation of the hospital stay. Our study team is highly experienced in conducting such interviews in hospitalized persons, which will assist in assuring retention, as well as avoiding any interference with ongoing medical care.

A.3.1.5. Post-hospitalization follow-up assessments: Several types of follow-up assessments will be conducted, as detailed below. These are all timed in relationship to zero-time, which is admission to the index hospitalization. Intercurrent illnesses and re-hospitalizations will be assessed at each follow-up time-point. If patients are hospitalized at the time of a scheduled follow-up assessment, we will wait for one month from hospital discharge to complete the follow-up assessment, to minimize the effects of acute illness on cognitive functioning. A detailed tracking system to track all participants over time will be developed. Some attrition is anticipated at each follow-up time point (due to mortality and losses to follow-up in this older population), as detailed in Core B. These attrition rates are accounted for in all power calculations below.

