A.3.1.5.1. Face-to-face interview or phone interviews at two weeks (Delirium group only): The purpose of this 10-15 minute face-to-face or phone interview is to repeat the delirium assessment to better assess the duration and persistence of the index delirium episode. This interview will be conducted at 2 weeks after hospital admission in patients who had delirium at any time during the index hospitalization. This interview will be conducted in all settings of care, including

hospital, home, assisted living, post-acute, or nursing home settings. We have extensive experience conducting interviews in all these settings, and the initial informed consent process will include these follow-up interviews. The two-week time period was selected for this interview, because previous work by our group has demonstrated the prognostic importance of the two week period: patients who resolve their delirium by 2 weeks regained their baseline functioning, whereas those with persistent delirium did not (Kiely 2006).

A.3.1.5.2. Retest face-to-face interviews at one and two months follow-up (Retest 1 and 2): The purpose of these 45 minute face-to-face interviews is to repeat our delirium assessments and neuro-psychological test battery to test for both the persistence of delirium and to evaluate retest (learning) effects. All subjects will be interviewed, although only a subset will have developed delirium while hospitalized. The Retest 1 interview (at 1 month) will assess for immediate learning or retest effects, particularly in the patients with normal cognitive functioning. The Retest 2 interview (at 2 months) will assess for delayed learning effects, which our preliminary results suggest are likely to be present in the delirious patients. Patients will also be asked about any rehospitalizations or intercurrent illnesses.

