A.3.1.5.3. Telephone follow-up interviews (4, 9, 15, 21 and 27): The purpose of these 10-15 minute telephone interviews is to assess delirium status, functional status, intercurrent illnesses, rehospitalizations, or death. These interim telephone interviews are considered essential to maximize retention, and to conduct brief cognitive testing, discover unreported hospitalizations, and track deaths. This interview will include a validated telephone version of the MMSE (Roccaforte 1992), which we have used in previous studies, telephone version of the CAM ([name] 1998, JGIM), ADLs/IADLs, recording of intercurrent illnesses, and dates and locations of hospitalizations.

A.3.1.5.4. Face-to-face follow-up interviews (6, 12, 18, then every 6 months up to 12 years): The major purpose of these 45 minute interviews is to obtain comprehensive neuropsychological and functional measures to rate our primary outcomes. These interviews will include the neuropsychological test battery, as well as the 3MS, digit span test, CAM, DSI, and MDAS ratings, ADLs, IADLs, SF36, Montreal Cognitive Assessment (MoCA), falls, sleep disturbance, smoking, alcohol, living situation, hearing and vision tests, intercurrent illnesses, and information on re-hospitalization, institutionalization, and death. If the subject is hospitalized at the time of the scheduled follow-up, then this interview will be postponed until one month after hospitalization to minimize the effects of the acute illness/hospitalization on the neuropsychological testing results. At each of these follow-up interviews, a surrogate will also be interviewed to complete the DQ, and proxy ratings of delirium and functional status (ADL, IADL) either face-to-face or by telephone.

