A.3.2.3.1. Delirium presence: The presence of delirium will be rated by the dichotomous yes/no diagnosis of delirium based on the validated Confusion Assessment Method (CAM) algorithm. This 4-item algorithm will be used to make a diagnosis of delirium based on DSM criteria. It has excellent psychometric properties, and is widely used in both research and clinical settings. The CAM rating will be completed at baseline, daily during each hospitalization, and at each follow-up assessment, based on information from the interview, 3MS (baseline/every 6 mos) or other cognitive screen (daily in hospital), digit span testing, DSI, and MDAS. Delirium by interviewer rating (CAM criteria) will be augmented with delirium rated as present by medical record review during the index hospitalization, since delirium can occur between interviews. For this study, we are assuming a delirium rate of at least 25% for the surgical cohort. We are also assuming that the vast majority of delirium occurs (or at least begins) in the hospital setting; delirium is rare in community settings. The Delirium Symptom Interview (*Albert 1992*) will be used to rate delirium symptoms and is useful to help with the completion of the CAM rating. This is a brief instrument that includes both questions asked directly of the patient and a series of structured observations. It is used specifically to determine the presence or absence of eight key features of delirium, as originally defined by the DSM-III criteria. Use of this method in conjunction with the CAM has been previously described (*Simon 2006*). For hospitalizations during follow-up, a validated chart rating of delirium (*[name] 2005*) will be completed.

A.3.2.3.2. Delirium severity: Delirium severity will be rated with the widely-used Memorial Delirium Assessment Scale (*Breitbart 1997*), a 10-item scale that uses information from the MMSE and structured observations to rate delirium severity. Each item is rated as 0-3, to generate a 0-30 scale (30=most severe).

A.3.2.3.3. Delirium duration and recurrence: Delirium duration will be determined as the total number of delirium-days (as rated by a positive CAM rating) during hospitalization in the

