study period; this variable will include only days of delirium by direct delirium assessments. Daily delirium ratings will occur only during hospitalization. To better assess the duration of the index delirium episodes, we will also conduct a face-to-face or phone interview with the patient at 2 weeks after hospital admission in patients who had delirium during the index hospitalization. Delirium recurrence will be determined as the total number of delirium episodes, which must be separated in time by at least 48 hours. Delirium recurrence can be counted for any delirium episode, including those determined by direct interviews, telephone or chart review. Recurrent and persistent delirium will be handled as time-varying covariates in secondary analyses.

A.3.3. Outcome Measures:

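### Nothing in the protocol keeps index delirium status from the interviewer who later rates the primary cognitive and functional outcomes, although one cross-trained staff pool does both jobs

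*Protocol*

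**What the plan says.** **Staff.** Protocol A.3.1.1 describes one body of research nurses and interviewers who "will undergo intensive training, following standardized procedures, in all questionnaires and research methods". The reliability assessments are there to "verify consistency of all staff on the primary outcomes (including the neuropsychological test battery and functional outcomes), as well as key risk factor variables", and the same sentence names the delirium assessment among those variables.

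**Exposure.** Under A.3.1.4, on admission "the patient will be seen by the study team in the hospital, and will undergo daily 10-15 minute interviews", which include the CAM, DSI and MDAS. No separate hospital team is named. Under B.5.2, when an interviewer finds delirium the study places a visible flag on or near the chart and updates it daily. A.3.1.5.1 then sets a further contact for the delirium group alone: "This interview will be conducted at 2 weeks after hospital admission in patients who had delirium at any time during the index hospitalization".

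**Outcome.** The main purpose of the six-monthly sessions in A.3.1.5.4 is to "obtain comprehensive neuropsychological and functional measures to rate our primary outcomes". Their content is given there as: "These interviews will include the neuropsychological test battery, as well as the 3MS, digit span test, CAM, DSI, and MDAS ratings, ADLs, IADLs, SF36". Table 2 lists the neuropsychological battery, ADL, IADL and SF-36 physical functioning as primary outcomes, with ADL and IADL taken from patient or family interview.

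**Masking.** No section separates hospital raters from outcome interviewers, withholds index delirium status, or describes the outcome assessor as masked.

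**The concern.** Project 1 tests whether delirium leads to greater decline, and the staff know this. If the person scoring a follow-up session knows that the patient was delirious in hospital, expectation can enter the score. The baseline assessment cannot be affected, because A.3.1.3 completes it before the surgical admission. Every later score can be.

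A downward shift confined to the delirium group would look like decline from baseline, which is the contrast in Hypothesis 1. Baseline adjustment would not remove it. Nor would the six-monthly inter-rater checks, since two raters who both know the history can agree and share the bias. A larger sample would only estimate the biased difference more precisely.

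**Working it through.** **1. Routes by which index delirium could become known**

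| Route | Where | What the text supports |
|---|---|---|
| Same person rates delirium and later tests the patient | A.3.1.1, A.3.1.4 | Possible; neither stated nor prevented |
| Flag at the chart during the stay | B.5.2 | Index delirium is on open display on the ward |
| Two-week contact | A.3.1.5.1 | Exists only for delirium patients, so a visible entry identifies them; the protocol does not say whether follow-up interviewers see it |
| CAM, DSI, MDAS at follow-up | A.3.1.5.4, A.3.2.3.1 | Given to everyone and rate current state; not a route |

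**2. Which outcomes are exposed.** ADL and IADL are scored 0, 1 or 2 per activity (unable, with help, without help; A.3.3.2) from interview, so some judgement enters. The neuropsychological battery is performance-based and standardized, so it is less open to expectation, though not immune.

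**3. Which contrast is affected.** Let *b* be a constant shift in every post-baseline score of the delirium group.
- Change from baseline to 18 months: the group difference moves by *b* − 0 = *b*.
- Difference between two post-baseline visits: it moves by *b* − *b* = 0.
- Straight line through visits at 0, 1, 2, 6, 12 and 18 months (complete data, equal weights): mean time = 39/6 = 6.5; Σ(t − 6.5)² = 509 − 6 × 42.25 = 255.5; Σ over post-baseline visits of (t − 6.5) = 39 − 32.5 = 6.5. The slope moves by (6.5/255.5)*b* = 0.0254*b* per month, or about 0.46*b* over 18 months.

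Table 3 names a time-by-delirium interaction as the effect of interest. How much of *b* enters it depends on how time is coded.

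**4. The plan's own power figures (B.1.1), for scale.** There are 400 complete cases with 25% delirium, so 100 v 300; alpha 5%, taken as two-sided.
- SE = √(1/100 + 1/300) = 0.115 SD.
- Power at 0.33 SD: 81.5% (normal) or 81.4% (t). The stated figure of more than 80% reproduces.
- Power at 0.61 SD: 99.96%. The stated 100% reproduces.

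**5. Illustration under an assumed shift.** The documents give no value for *b*. With no true effect, the false-positive rate for change from baseline is Φ(*b*/0.115 − 1.96) + Φ(−*b*/0.115 − 1.96):

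| Assumed *b* (SD) | False-positive rate | Share of 0.33 SD |
|---|---|---|
| 0 | 5% | 0% |
| 0.05 | 7% | 15% |
| 0.10 | 14% | 30% |
| 0.15 | 25% | 45% |
| 0.20 | 41% | 61% |

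**The case against.** The strongest reply is that the point rests on silence. Cross-training does not assign one person to both jobs for a patient. A.3.1.5 says only that a tracking system will be developed, not what interviewers see on it. This stands: a reader might infer that the outcome assessor is known to be unmasked, and the text does not establish that. What remains is that a plan followed to the letter permits it. Who tests whom, and with what information, is study conduct, which an analysis plan would not normally settle.

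A reader might also infer from "These interviews will include the neuropsychological test battery, as well as the 3MS, digit span test, CAM, DSI, and MDAS ratings, ADLs, IADLs, SF36" that rating delirium in the outcome session reveals the exposure. It does not. A.3.2.3.1 says "The CAM rating will be completed at baseline, daily during each hospitalization, and at each follow-up assessment", for every participant, and the rating concerns current state. Those ratings can count towards recurrence, a separate predictor, but they do not disclose the index episode.

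Three further replies stand in part. Index delirium also includes cases found by chart review, which an interviewer need not know; this dilutes the problem. Scripted tests and six-monthly reliability checks limit drift but do not mask. A constant shift leaves the slope among later visits untouched, as shown above, so it would be wrong to say that every delirium-by-time estimate is biased.

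Finally, this revision is dated September 2019 and says that many participants have left. Much of the early follow-up may be complete, and a change now cannot repair it.

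**Conclusion.** The concern holds in a limited form. The protocol uses one cross-trained staff pool for exposure and outcome, flags delirium openly in hospital, and schedules a delirium-only contact, with no provision to keep index delirium from the outcome interviewer. This leaves a possible bias in the delirium difference in change from baseline, most plausibly in ADL and IADL and less so in the battery. The likely direction favours the hypothesis.

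Its size cannot be derived from the documents. The table in the working rests on assumed shifts, a true effect of zero and a simple two-group comparison; it shows scale and is not an estimate. No sample-size or power figure changes. This is an inexpensive improvement to study conduct, not evidence that bias has occurred.

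**What to change.** Amend A.3.1.1 and A.3.1.5 for all remaining outcome interviews, in delirium and non-delirium patients alike:

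1. Do not show hospital CAM results or the two-week contact on the tracking or tablet screens used for follow-up.
2. Where staffing allows, assign an existing interviewer who did not do that patient's hospital or two-week assessments.
3. Complete the battery, ADL, IADL and SF-36 before the hospitalization questions, which may prompt the patient to mention the index episode.
4. Have the interviewer record whether index delirium became known, and run a sensitivity analysis on that record.

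Record the date on which the change takes effect, so that any step in the series can be examined.

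**Cost.** A display setting, an instrument order, one extra item per interview and some scheduling effort, with slightly less interviewer continuity. The protocol gives no interviewer numbers, so step 2 may not always be possible; the other steps do not depend on it. Masking will stay incomplete because patients or proxies may disclose delirium, which is the reason for step 4.

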We proposed a 7 year prospective observational study which got extended to 12 years, including 6 months for initiation, 30 months for patient enrollment, 42 months (additional) to complete all patient follow-ups, and 6 months for statistical analyses and manuscript preparation. The proposed study will enroll 550 elective non-cardiac surgical patients, each of whom will be followed prospectively for a minimum of 18 months and up to 72 months initially and then extended to 12 years, after their initial hospitalization. All patients will undergo a baseline evaluation prior to hospitalization, including neuropsychological and frailty testing. The primary outcomes for this project are cognitive decline, based on a neuropsychological test battery, and functional decline. When admitted for the index hospitalization, patients will be assessed daily for the development of delirium, the major predictor variable. Subsequently, each patient will be followed prospectively for a minimum of 18 months or until death or termination of the project period with a face-to-face interview at 1 and 2 months, telephone interviews at 4, 9, 15, 21 and 27 months and face-to-face interviews including neuropsychological testing every 6 months up to 12 years. Medical records for each patient from all hospitalizations (including outside hospitals) will be reviewed at the end of their index hospitalization, after each subsequent hospitalization, after their final study **interview or end** of data collection (12 years)--to identify any hospitalizations (including recurrent delirium and repeat surgeries), intercurrent illnesses, new diagnoses, unidentified hospitalizations, or unreported deaths.

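### Delirium duration is counted over the whole study period rather than the index stay, and the rules on how later hospitalizations are assessed conflict, so days that follow cognitive decline can enter this predictor

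*Protocol*

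**What the plan says.** All references are to the Protocol.

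- **Definition (A.3.2.3.3).** "Delirium duration will be determined as the total number of delirium-days (as rated by a positive CAM rating) during hospitalization in the". The same sentence then names its window and limits what counts towards the total: "study period; this variable will include only days of delirium by direct delirium assessments".
- **Role (A.3.2.2, Table 2).** Duration is among the major predictors. Table 2 lists it together with persistence, for SA2, and also as a secondary outcome.
- **Index stay (A.3.1.4).** "The initial hospitalization during the study period will be considered the index hospitalization". A readmission within 24 hours counts as the same stay.
- **Who is assessed directly, and when.** A.3.2.3.1: "The CAM rating will be completed at baseline, daily during each hospitalization, and at each follow-up assessment". A.3.1.4: the principal investigator is notified "whenever an enrolled study patient is admitted to the BIDMC or BWH". A.2: "When admitted for the index hospitalization, patients will be assessed daily for the development of delirium, the major predictor variable".
- **Later stays.** A.3.2.3.1: "For hospitalizations during follow-up, a validated chart rating of delirium" will be completed. A.3.1.5.5 likewise has delirium in subsequent hospitalizations assessed from the chart.
- **Later delirium in the models (A.3.2.3.3).** "Recurrent and persistent delirium will be handled as time-varying covariates in secondary analyses". Duration is not named there.

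**The concern.** Cognition is measured at baseline, at 1, 2, 6, 12 and 18 months, and then every six months up to 12 years (A.3.3.1). A patient who has declined may be more likely to become delirious when readmitted. If those days are added to a total that is then used to predict the same patient's decline, part of the predictor is a consequence of the outcome. A relation between more delirium days and faster decline could then appear even if index delirium had no effect.

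There is also a risk of uneven measurement. On the literal reading, a readmission to one of the two study hospitals can yield directly assessed days. A readmission elsewhere is known only from records and cannot.

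**Working it through.** **Step 1. Compare the rules.**

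| Question | Reading A: later days can count | Reading B: later days cannot count |
|---|---|---|
| Window for duration | Study period (A.3.2.3.3), of which the index stay is only the first hospitalization (A.3.1.4) | The two-week interview in A.3.2.3.3 serves the index episode |
| Daily CAM | Each hospitalization (A.3.2.3.1); alert for any admission to either study hospital (A.3.1.4) | Index hospitalization (A.2) |
| Method in later stays | Direct CAM, which satisfies the limit to direct assessments | Chart rating (A.3.2.3.1, A.3.1.5.5), which that limit excludes |
| Time-varying handling | Names recurrent and persistent delirium only | Table 2 pairs duration with persistence, so the rule might be stretched to cover duration |

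No sentence says which column governs. A.3.2.3.1 contains both the daily-CAM rule and the chart-rating rule. Where the authors mean the index stay they say so elsewhere, for example for the chart-review supplement to the CAM in A.3.2.3.1. The duration sentence carries no such limit.

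**Step 2. What does not depend on duration.** No figure in the Protocol uses it. Hypothesis 1 (B.1.1) compares delirium with no delirium at 18 months. With 400 completers and 25% delirium, that is 400 × 0.25 = 100 against 300. Two-sided 5% power is 0.9996 at 0.61 SD (stated 100%) and 0.815 at 0.33 SD (stated above 80%). Both statements reproduce, and neither involves duration.

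**Step 3. Illustration over a fixed interval.** Apart from n = 400 and 25% index delirium, every input is assumed:

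- days per episode = 1 + Poisson(1), mean 2;
- cognitive change s is standard normal and unrelated to index days (the null);
- 30% of patients are rehospitalized;
- delirium in the later stay has logit(p) = −1.4 − b·s, about 20% at s = 0;
- predictor = index days + counted later days, as one fixed total; 1,000 replicates per setting.

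Rejection rate of a nominal 5% test:

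| b (odds ratio per SD of decline) | No later days counted | Half counted | All counted |
|---|---|---|---|
| 0 (1.0) | 0.057 | 0.041 | 0.046 |
| 0.5 (e^0.5 = 1.65) | 0.037 | 0.066 | 0.148 |
| 1.0 (e^1 = 2.72) | 0.063 | 0.135 | 0.367 |

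The simulation error at 5% is √(0.05 × 0.95 / 1000) = 0.0069. Rates between 0.036 and 0.064 (0.05 ± 1.96 × 0.0069) are therefore compatible with 5%. Inflation needs two things together: later days must be counted, and later delirium must depend on decline.

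**Step 4. Illustration by length of follow-up.** Assumed: n = 400, 25% index delirium, mean 2 days per episode, 0.3 readmissions a year with 70% to study hospitals, 20% delirium per readmission, odds rising 2- or 3-fold per SD of decline, and no effect of index days on slope.

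| Follow-up | Index days only (OR 2 / OR 3) | Whole-period days (OR 2 / OR 3) |
|---|---|---|
| 1.5 years | 4.8% / 5.0% | 4.9% / 4.0% |
| 3 years | 6.0% / 4.5% | 7.1% / 10.2% |
| 6 years | 4.5% / 4.4% | 26.7% / 58.4% |

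The two illustrations agree in direction but not in size. The first ties later delirium to the patient's whole change, including change after the readmission, and so leans high. The second shows nothing at 18 months and growth thereafter.

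**The case against.** The best defence is that the specific rules already confine duration to the index stay. Only direct assessments count, later stays are chart-rated, A.2 places daily assessment in the index stay, and the two-week interview is about the index episode. Read together, later stays add no days. This is a fair reading and may be what was meant. It does not settle the matter, because it requires the daily-CAM rule in A.3.2.3.1 and the study-period window to be set aside, and nothing says they should be.

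Three further points stand and limit the finding:

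- No section says that duration enters a model as a time-fixed covariate. Table 3 names delirium and delirium severity, not duration, for Project 1 Aims 1-2. How duration is modelled may properly be left to an SAP.
- The simulation inputs have no source in the Protocol. A 70% share of readmissions to study hospitals sits uneasily with A.3.1.5.5, which expects a large number of different hospitals.
- The longest cognitive trajectory considered in B.1.1 is 36 months. The six-year figures describe an analysis that the Protocol does not specify, although follow-up does run to 12 years.

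A reader might infer that the predictor definitely contains delirium arising after the decline, or that the Protocol deliberately measures duration differently by hospital. The documents support neither. Both follow only on the literal reading, and no section draws a distinction by hospital.

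**Conclusion.** The definition is internally inconsistent and should be corrected. As written, it permits delirium days from later study-hospital readmissions to count towards a major predictor. It does not establish that they will. Even on the wide reading, only days that fall after a given cognitive assessment are out of order with respect to that assessment.

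The primary 18-month comparison by presence of delirium is untouched. The exposure lies in duration analyses over the extended follow-up, if later days are summed into a time-fixed total. Under that condition and the assumed inputs of Step 4, false-positive rates are 4% to 5% at 18 months, 7% to 10% at three years and 27% to 58% at six years, against 4% to 6% for index days alone. These are illustrations, not estimates for this cohort. The correction is worth making under either reading. If index-only was intended, the text misstates it. If a cumulative measure was intended, its time order is unprotected.

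**What to change.** 1. In A.3.2.3.3, replace the study-period window for duration with the index hospitalization, including readmission within 24 hours as A.3.1.4 defines it.
2. In A.3.2.3.1, reconcile the daily CAM in each hospitalization with A.2 and with the chart-rating sentence, so that one rule covers later stays. Make clear whether the admission alert in A.3.1.4 leads to daily interviews after the index stay.
3. Let later in-hospital delirium enter only through the time-varying recurrent and persistent terms already planned, ascertained by the chart method at every hospital.
4. If a cumulative duration is wanted as a secondary measure, define it as time-updated, counting only days before each cognitive assessment.

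The cost is a few sentences. Index-stay CAM days are already collected (A.3.1.4), and records from later hospitalizations are already to be requested and abstracted (A.3.1.5.5), so no new data are needed.
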